## **Statistical Methods**

## General principles

This Statistical Analysis Plan describes the methods for analysis of the effect of traumafocused therapies for individuals with PTSD and psychosis on primary, secondary, and adverse outcomes. Other analyses outlined in the published protocol, such as costeffectiveness analysis, will be described and published separately.

All analyses will be completed in R (version 4.4.2) unless stated otherwise. All tests are two-sided and a significance level of  $\alpha$ =0.05 is adopted.

Data will be analysed following the intention-to-treat principle, ensuring all randomized participants are analysed in their assigned groups, regardless of adherence or missing data. Missing data will be treated as missing at random.

Statistical analyses will be carried out by [name], under supervision of dr. [name], dr. [name], dr. [name], and prof. dr. [name]. An independent statistician will be consulted throughout the analysis process.

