## Primary Outcome Analysis

To evaluate changes in researcher-rated PTSD symptom severity over time and treatment differences, a LMM will be fitted using restricted maximum likelihood (REML) estimation. The primary model includes baseline scores as covariate, treatment condition as fixed effect, time as categorical variable, an interaction term between treatment condition and time, and a random intercept for each participant to account for within-subject correlations. An interaction effect between treatment condition and time variables would indicate differential treatment effects over time. To appropriately model the within-subject correlation of repeated outcome measures across unequally spaced timepoints, an unstructured covariance matrix will be applied to the residuals in the LMM. This results in the following model equation:

$$Y_{ij} = \beta_0 + \beta_1 \cdot Baseline_i + \sum_{k=1}^{3} \beta_{2k} \cdot Group_{ik} + \sum_{l=1}^{3} \beta_{3l} \cdot Time_{jl} + \sum_{k=1}^{3} \sum_{l=1}^{3} \beta_{4kl} \cdot (Group_{ik} \times Time_{jl}) + u_i + \varepsilon_{ij}$$

Where:

- *Yii*: Outcome for participant *i* at timepoint *j*
- *Baseline*i: Baseline outcome value for participant *i*
- *Groupik*: Dummy-coded treatment condition indicators (3 dummies: CR, PE, EMDR; WL = reference)
- *Timejl*: Dummy-coded time indicators (3 dummies: midtreatment, posttreatment, 6-month follow-up; baseline = reference)
- $Group_{ik} \times Time_{il}$ : Group-by-time interaction terms
- $u_i$ : Random intercept for participant i
- $\varepsilon_{ii}$ : Residual error
- Fixed effects:
  - Intercept  $\beta_0$ : Mean outcome at baseline for WL
  - $\circ$   $\beta_1$ : Effect of individual baseline outcome value (covariate)
  - $\circ$   $\beta_{2k}$ : Group main effects at baseline, compared to WL
  - $\circ$   $\beta_{3l}$ : Time effects for WL (how outcomes change over time within WL)
  - $\circ$   $\beta_{4kl}$ : Additional group-specific changes over time relative to WL

To quantify the magnitude of treatment effects, effect sizes will be estimated for timepoints T3 and T6 based on the mean pre-post change (i.e. baseline scores vs. follow-up scores) of the treatment condition minus the mean pre-post change of WL, divided by the pooled pretest standard deviation 

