## Secondary and Tertiary Outcome Analyses

For continuous outcomes, LMMs with similar methodology as the primary outcome analysis will be applied. For dichotomous outcomes (e.g., clinician-rated presence of PTSD diagnosis) generalized linear mixed models (GLMMs) with a logit link function will be used, in line with the following model equation:

$$\log\left(\frac{\Pr(Y_{ij}=1)}{1-\Pr(Y_{ij}=1)}\right) = \beta_0 + \beta_1 \cdot Baseline_i + \sum_{k=1}^3 \beta_{2k} \cdot Group_{ik} + \sum_{l=1}^3 \beta_{3l} \cdot Time_{jl} + \sum_{k=1}^3 \sum_{l=1}^3 \beta_{4kl} \cdot (Group_{ik} \times Time_{jl}) + u_i + \varepsilon_{ij}$$

Here, the left-hand side of the model equation indicates the log-odds of the outcome being 1 (e.g., no longer meeting PTSD diagnosis criteria).

The trial protocol specified Generalised Estimating Equations (GEE) would be used to analyse dichotomous outcomes. This plan has been updated to employ GLMMs, as they allow explicit modeling of random effects and individual-level variability, while offering more robust performance when handling missing data under missing at random (MAR) assumptions, which better suits our study's anticipated data structure.

Similar to the primary analysis, effect size of continuous outcomes will be estimated with  $d_{ppc2}$ . For dichotomous outcomes, odds ratios (ORs) will be calculated from the fitted GLMM. Here, exponentiated model coefficients will be interpreted as odds ratios comparing the odds of the outcome between treatment arms and timepoints.

In addition to testing treatment effect on primary and secondary outcomes over time, post-hoc pairwise comparisons between treatment groups and the waitlist control group will be conducted at each timepoint using estimated marginal means with Bonferroni correction to adjust for multiple comparisons.

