# Sensitivity Analyses

To evaluate the robustness of the findings of the primary outcome analysis, the following sensitivity analyses will be performed:

- Per-protocol analysis: estimating treatment effects among participants who completed their allocated therapy (i.e., participants who completed all 16 therapy sessions or participants who met criteria for early completiona).
- Multiple imputation sensitivity analysis: compare primary model with only assessment completers to model with missing outcome data imputed to examine if data is missing at random (MAR). Missing data in the outcome variable will be handled using multiple imputation via chained equations.

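### The SAP says every randomised participant is analysed whatever data are missing, but its models cannot use a participant whose baseline score on that scale is missing

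*SAP*

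**What the plan says.** - **General principles:** the intention-to-treat analysis is described as "ensuring all randomized participants are analysed in their assigned groups, regardless of adherence or missing data", followed by "Missing data will be treated as missing at random". No procedure is named for a missing covariate.
- **Primary Outcome Analysis:** "a LMM will be fitted using restricted maximum likelihood (REML) estimation", and "The primary model includes baseline scores as covariate". The model equation has the participant's baseline value on the right-hand side. The time factor is coded as "3 dummies: midtreatment, posttreatment, 6-month follow-up; baseline = reference", so T0 also appears as a response time point.
- **Secondary and Tertiary Outcome Analyses:** for continuous outcomes, "LMMs with similar methodology as the primary outcome analysis will be applied". The logit model for dichotomous outcomes also carries the baseline term.
- **Sensitivity Analyses:** "Missing data in the outcome variable will be handled using multiple imputation via chained equations". This section concerns the robustness of the primary outcome analysis only.

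**The concern.** A mixed model fitted by likelihood uses whatever responses a participant has, and under missing at random that is sound. It does not do the same for covariates, because the likelihood is conditional on them. The baseline score is constant within a participant, so if it is missing, every row of that participant is unusable for that outcome, including complete follow-up. Software will drop the rows or stop with an error; the data go unused either way.

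The statement about all randomised participants is therefore not a property of the models that follow it. Taken literally, the plan could leave out a different set of people for each scale while the report says that everyone was analysed. The loss is avoidable, and fixing a rule now also removes an analyst's choice later.

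**Working it through.** **1. The plan's own figure.** Inputs from Sample Size Calculation: two-sided α 0.05, power 0.80, d = 0.5, ρ = 0.45, m = 3 follow-ups, attrition 20%.

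- One measurement per person: 2 × ((1.96 + 0.842)/0.5)² = 62.8 per arm.
- Factor for the mean of three follow-ups: [1 + (m − 1)ρ]/m = (1 + 2 × 0.45)/3 = 0.6333.
- 62.8 × 0.6333 = 39.8, rounded up to 40; 40/0.80 = 50 per arm.

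The stated 50 per arm is reproduced, on a variance without baseline adjustment.

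**2. Who enters the model.** REML random-intercept models were fitted to simulated data: 200 participants in four arms, 10 without a baseline score, follow-up complete.

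| Model | Participants used | Follow-up rows used (of 600) |
|---|---|---|
| Baseline covariate, T0 also a response | 190 | 570 |
| Baseline covariate, follow-up rows only | 190 | 570 |
| T0 as a response, no baseline covariate | 200 | 600 |

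Keeping T0 as a response row does not rescue anyone while the covariate stays in the model. The loss of rows does not depend on the covariance structure.

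**3. Size.** The SAP gives no rate, so the missing fraction f is assumed, and taken as unrelated to arm and to the 20% attrition.

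- Standard error ratio = 1/√(1 − f).
- Power on the SAP's basis = Φ(0.5/√(2 × 0.6333/(40(1 − f))) − 1.96).

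| f | Participants lost of 200 | Rise in SE | Power |
|---|---|---|---|
| 0 | 0 | 0 | 80.2% |
| 2% | 4 | 1.0% | 79.4% |
| 5% | 10 | 2.6% | 78.2% |
| 10% | 20 | 5.4% | 76.0% |
| 20% | 40 | 11.8% | 71.0% |

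The power column applies to a scale only if d = 0.5 and ρ = 0.45 hold for it, which the SAP does not say. The SE column does not need those values.

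**4. Filling the covariate with the pooled mean.** With the same ρ, the variance of the follow-up mean per person is 0.6333 without baseline adjustment and 0.6333 − 0.45² = 0.4308 with it. A filled participant contributes at the first value, the others at the second. The SE ratio against no missing baselines is √((0.4308 + 0.2025f)/0.4308), a rise of 1.2%, 2.3% and 4.6% at f = 5%, 10% and 20%. Simulation (linear analysis of covariance of the mean of three follow-ups, four arms of 40, 8,000 trials per rate) gave about 1.1%, 2.2% and 4.5%, with type I error between 4.4% and 5.4%. A repeat gave 1.1%, 2.3% and 4.9%.

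**5. T0 as a response only.** This keeps everyone, but its precision depends on how T0 is modelled. If each arm has its own T0 mean and the contrast is change from T0, the variance per person is 0.6333 + 1 − 2 × 0.45 = 0.7333, an SE √(0.7333/0.4308) = 1.30 times that of the baseline-adjusted analysis. A common T0 mean across arms avoids that loss.

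**The case against.** The strongest reply is that nothing in the SAP shows a missing baseline. The CAPS-5 probably has none, if it establishes the PTSD that the trial population must have. PTSD diagnosis comes from the same interview, so among the primary and secondary outcomes only the ITQ score is left exposed, and the tertiary outcomes are described as exploratory. This stands, and it keeps the point small.

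It can also be said that the sentence in General principles is a statement of principle, and that the imputation may be read to cover the baseline, since the SAP treats baseline as a value of the outcome. That reading is possible, but it helps only in a sensitivity analysis of the primary outcome. The main analyses, and all secondary and tertiary outcomes, stay without a rule.

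A reader might infer that the SAP orders such participants to be deleted. It does not; the exclusion follows from the equations. A reader might also quote a fall in power from 92.6% (to 91.3% at 5% missing), which is the series for a baseline-adjusted analysis. The SAP planned on 80% without that adjustment, so the series starting at 80.2% is the relevant one.

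Finally, the mean fill was checked only for a linear analysis of averaged follow-ups. It was not checked for the logit model, where the odds ratio depends on covariate adjustment, nor for the primary model as written, with T0 both covariate and response. This stands and limits the fix.

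**Conclusion.** The inconsistency is real and minor. The models cannot include a participant whose baseline on the scale is missing, and no section supplies a remedy for the main analyses. No stated number in the SAP is wrong, and the sample size is unaffected.

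The size rests on an assumed rate: a 2.6% rise in SE at 5% missing and 5.4% at 10%, for the affected scale only; with no missing baselines, nothing changes. The likely places are the ITQ and the tertiary scales, including the baseline composite of adversities and revictimisation that Safety Analysis builds from weekly smartphone reports.

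A reader might infer that the treatment comparisons would be biased or the primary result compromised. The document does not support either. If baseline is measured before randomisation, exclusion for a missing baseline cannot depend on arm, and the cost is precision. The SAP does not state that order, so it remains an assumption, and it also underlies the mean fill.

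**What to change.** For the linear mixed models in Primary Outcome Analysis and for the continuous outcomes in Secondary and Tertiary Outcome Analyses, adopt one of two rules.

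- **Keep baseline as a covariate.** Add: where a baseline score used as a covariate is missing, it is replaced by the mean of that score over all randomised participants, arms pooled and without use of follow-up data; only the covariate is filled, never a T0 response row.
- **Model T0 only as a response, without the baseline covariate.** This keeps everyone and also ends the double use of T0 in the primary model. The SAP should then give all arms a common T0 mean, for the reason in step 5 of the working.

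In either case, reword General principles so that it claims only what the models deliver, and confirm that T0 is completed before randomisation. The logit model needs its own statement on missing baselines, since the mean fill has not been shown to be valid there. Nor does the fill supply a baseline for the d_ppc2 effect size, which needs observed change and the pretest standard deviation.

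The first rule costs one or two sentences and about one line of code per outcome. Its small downside is that filled participants get no individual baseline adjustment. The second costs a rewritten model equation.

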## Primary Outcome Analysis

To evaluate changes in researcher-rated PTSD symptom severity over time and treatment differences, a LMM will be fitted using restricted maximum likelihood (REML) estimation. The primary model includes baseline scores as covariate, treatment condition as fixed effect, time as categorical variable, an interaction term between treatment condition and time, and a random intercept for each participant to account for within-subject correlations. An interaction effect between treatment condition and time variables would indicate differential treatment effects over time. To appropriately model the within-subject correlation of repeated outcome measures across unequally spaced timepoints, an unstructured covariance matrix will be applied to the residuals in the LMM. This results in the following model equation:

$$Y_{ij} = \beta_0 + \beta_1 \cdot Baseline_i + \sum_{k=1}^{3} \beta_{2k} \cdot Group_{ik} + \sum_{l=1}^{3} \beta_{3l} \cdot Time_{jl} + \sum_{k=1}^{3} \sum_{l=1}^{3} \beta_{4kl} \cdot (Group_{ik} \times Time_{jl}) + u_i + \varepsilon_{ij}$$

Where:

- *Yii*: Outcome for participant *i* at timepoint *j*
- *Baseline*i: Baseline outcome value for participant *i*
- *Groupik*: Dummy-coded treatment condition indicators (3 dummies: CR, PE, EMDR; WL = reference)
- *Timejl*: Dummy-coded time indicators (3 dummies: midtreatment, posttreatment, 6-month follow-up; baseline = reference)
- $Group_{ik} \times Time_{il}$ : Group-by-time interaction terms
- $u_i$ : Random intercept for participant i
- $\varepsilon_{ii}$ : Residual error
- Fixed effects:
  - Intercept  $\beta_0$ : Mean outcome at baseline for WL
  - $\circ$   $\beta_1$ : Effect of individual baseline outcome value (covariate)
  - $\circ$   $\beta_{2k}$ : Group main effects at baseline, compared to WL
  - $\circ$   $\beta_{3l}$ : Time effects for WL (how outcomes change over time within WL)
  - $\circ$   $\beta_{4kl}$ : Additional group-specific changes over time relative to WL

To quantify the magnitude of treatment effects, effect sizes will be estimated for timepoints T3 and T6 based on the mean pre-post change (i.e. baseline scores vs. follow-up scores) of the treatment condition minus the mean pre-post change of WL, divided by the pooled pretest standard deviation 

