#### Secondary objective

Secondary objectives are to compare the effects of CR, PE, EMDR, to WL for researcherrated severity of PTSD symptoms at the separate time-points (i.e. mid-treatment, posttreatment, and at 6-month follow-up) and to test the effects (over time and at each timepoint) for clinician-rated presence of PTSD diagnosis according to the DSM-5 criteria, and self-reported severity of complex PTSD symptoms.

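### The primary LMM imposes one baseline slope on every visit; if the true slopes differ, the T6 contrasts can lose precision, and under arm-dependent dropout they can be biased

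*SAP*

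**What the plan says.** Under Primary Outcome Analysis the SAP writes that "The primary model includes baseline scores as covariate, treatment condition as fixed effect, time as categorical variable". The sentence continues with "an interaction term between treatment condition and time, and a random intercept for each participant". The only interaction is therefore group by time. In the equation the baseline coefficient carries no visit index, and its legend reads "Effect of individual baseline outcome value (covariate". The correlation between repeated measures is left free: "an unstructured covariance matrix will be applied to the residuals in the LMM". Time is coded with "3 dummies: midtreatment, posttreatment, 6-month follow-up; baseline = reference", so T0 appears as a level of the outcome as well as a covariate.

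Three other places bear on this. The Secondary objective asks for each therapy against waitlist on CAPS-5 "at the separate time-points (i.e. mid-treatment, posttreatment, and at 6-month follow-up". General principles says "Missing data will be treated as missing at random". For the other continuous outcomes, "LMMs with similar methodology as the primary outcome analysis will be applied".

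**The concern.** A single baseline coefficient assumes that one point of baseline CAPS-5 predicts the same difference at 7 weeks, 3 months and 6 months. The rest of the model makes no such equality assumption across visits, and the SAP gives no reason for making it here.

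If the baseline association weakens with time, the common slope is too steep for T6, and T6 is over-adjusted. Two things can follow:

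- The T6 contrast is noisier than the data allow.
- If the participants still observed at T6 differ in baseline severity between arms, the wrong slope corrects that difference by the wrong amount. Dropout driven by baseline is missing at random given a variable in the model, so a reader would expect the analysis to handle it.

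The contrasts at stake are the per-visit comparisons with waitlist, T6 above all, for CAPS-5 and for every outcome that inherits the model.

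**Working it through.** **Inputs from the SAP:** effect 0.5 SD, correlation 0.45, three follow-ups, 20% attrition, 50 per arm, two-sided 5%, 80% power.

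**Inputs assumed, because the SAP gives none:** baseline correlations with T2/T3/T6, correlations among follow-ups, equal SDs unless stated, and dropout log-odds of 1 per baseline SD.

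**1. The SAP's own figure.** 2(1.960+0.842)²/0.5² = 62.8. Multiplied by (1+2×0.45)/3 = 0.6333, this gives 39.8, rounded up to 40. Then 40/0.80 = 50 per arm, as stated. The calculation uses the mean of three follow-ups without baseline adjustment, so the sample size does not depend on this point.

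**2. Where the common slope settles (outcome rows T2, T3, T6 only).** Let s be the vector of true slopes, R the follow-up correlation matrix and Σ = R − ss′. With complete data the common slope is b = (1′Σ⁻¹s)/(1′Σ⁻¹1). The T6 contrast has variance proportional to 1 − 2b·s₆ + b², against 1 − s₆² with its own slope. The ratio is 1 + (b − s₆)²/(1 − s₆²).

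| Baseline slopes T2/T3/T6 | Follow-up correlation | b | T6 variance ratio |
|---|---|---|---|
| 0.45/0.45/0.45 | any | 0.45 | 1.00 |
| 0.55/0.45/0.35 | 0.6 | 0.474 | 1.02 |
| 0.70/0.45/0.20 | 0.5 | 0.600 | 1.17 |
| 0.70/0.45/0.20 | 0.6 | 0.655 | 1.22 |
| 0.70/0.45/0.20 | 0.7 | 0.771 | 1.34 |

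Example, third row: (0.600 − 0.20)²/(1 − 0.04) = 0.160/0.96 = 0.167.

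A simulation with 50 per arm and about 20% dropout unrelated to baseline used follow-up correlations 0.6/0.45/0.6 (T2-T3, T2-T6, T3-T6). T6 standard errors were 0.2355 (common slope) and 0.2138 (visit-specific) under steep decay, a variance ratio of 1.21. Under moderate decay they were 0.2075 and 0.2068, a ratio of about 1.01.

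**3. Bias at T6.** Let g be the arm difference in mean baseline among those still observed. To a first approximation the bias is (s₆ − b)·g. With the follow-up correlations just given, b is 0.467 under moderate and 0.582 under steep decay. With 20-25% lost by T6, g was about −0.23 when baseline drove dropout in the active arm only, and −0.47 when it acted in opposite directions.

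- Moderate decay, opposite directions: (0.35 − 0.467)×(−0.47) = 0.055. The large-sample fit (150,000 per arm) gave 0.057.
- Steep decay, active arm only: (0.20 − 0.582)×(−0.237) = 0.091. The fit gave 0.094.
- Steep decay, opposite directions: (0.20 − 0.582)×(−0.47) = 0.180. The fit gave 0.190.
- Baseline drives dropout equally in both arms: g is about 0, and there was no bias beyond sampling error under any slopes.
- Flat 0.45: no bias under any dropout pattern.

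A separate run with a follow-up correlation of 0.6 and about 20% dropout gave 0.03-0.09 SD (one arm only) and 0.06-0.16 SD (opposite directions) across the same two sets of slopes. Bias was at most 0.02 SD at T2 and 0.06 SD at T3 in the large-sample fits. With visit-specific slopes, T6 bias was at most about 0.01 SD in every scenario.

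**4. Cost when the slopes are equal.** T6 standard error was 0.192 (common) against 0.193 (visit-specific) with dropout unrelated to baseline. With dropout in opposite directions it was 0.203 against 0.207.

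**The case against.** The strongest case against is that a common-slope ANCOVA-type model is a legitimate, parsimonious choice. Under randomisation its contrasts are unbiased unless two conditions hold together: slopes differ by visit, and baseline-dependent dropout differs by arm. The SAP documents neither. That stands, and it rules out some stronger readings.

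- A reader might infer that the per-visit effects are biased and imprecise as planned. The only correlation in the SAP is 0.45, and with equal SDs that value gives neither loss nor bias.
- A reader might infer that any baseline-dependent dropout causes bias. It does not: equal dependence in all arms cancels in the contrast.
- A reader might take the unstructured covariance as a sign that the authors expect the baseline association to fade. The SAP says only that it models correlation across unequally spaced visits.
- A reader might extend the point to the primary objective. That concerns the effect over time, whereas the main exposure is in the secondary per-visit contrasts.

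Two parts of the objection do not carry. First, a constant correlation does not guarantee equal slopes, because slope is correlation times the SD ratio. With correlation 0.45 and assumed SD ratios 1.0/1.5/1.5 the slopes are 0.45/0.68/0.68. SDs can also work the other way: correlations 0.55/0.45/0.35 with ratios 1.0/1.2/1.5 give 0.55/0.54/0.525, nearly common. Second, the planned chained-equation imputation could allow visit-specific slopes, but its predictors are not stated, so it cannot be counted on as a check.

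It is also fair to object that adding the interaction to the printed equation alone would not work. T0 is there both a Time level and its own covariate, so that row is fitted exactly with slope 1 and no residual. The outcome rows must be settled first. All bias and variance figures above assume T2, T3 and T6 only.

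**Conclusion.** The point holds in conditional form. The model makes an equality assumption that the SAP does not justify and does not need.

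- If slopes differ by visit, T6 variance is about 2% larger under moderate decay and 17-34% larger under steep decay, the latter for assumed follow-up correlations of 0.5 to 0.7.
- If baseline-dependent dropout also differs by arm, T6 bias is about 0.03-0.09 SD in the one-arm case and 0.06-0.16 SD in the opposite-direction worst case (0.19 SD under the other follow-up correlations and heavier dropout). Its sign depends on which arm loses the more severe participants.
- If slopes are equal, there is no bias and no loss.

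The decay patterns and dropout strength are assumptions, and the upper figures need both to be strong. This is a worthwhile protection of the T6 contrasts and not a demonstrated error in the results.

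**What to change.** In the primary equation, and in the LMMs for all other continuous outcomes:

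1. Restrict the outcome rows to T2, T3 and T6. Time then has two dummies and T0 enters only as a covariate. Reword the definitions of the intercept and the group and time effects to match.
2. Add a baseline-by-time interaction, so that each follow-up visit has its own baseline slope.
3. State that estimated marginal means and the per-visit therapy-versus-waitlist contrasts are computed at the overall mean baseline.

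The cost is two extra parameters with 200 randomised participants, a small edit to the SAP and code, and no new data. When the slopes are equal, the simulated standard error rose by about 0.001 with dropout unrelated to baseline and by about 0.004 in the worst dropout pattern. The change should be made before outcome data are analysed, so that the term is not chosen in the light of the results.

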## Sample Size Calculation

A formal power analysis was conducted to determine the required sample size for the planned longitudinal intention-to-treat (ITT) analyses using linear mixed models (LMM).

Based on data from previous randomized controlled trials in this field , the calculation used the following parameters: significance level ( $\alpha$ ) of 0.05 (two-sided), power (1- $\beta$ ) of 0.80, expected correlation between repeated measures ( $\rho$ ) of 0.45, and 3 repeated follow-up assessments. The minimum detectable effect size was set at 0.5 (medium effect, compared to waiting list control), while accounting for an anticipated attrition rate of 20%. These calculations indicated that 50 participants would be needed in each study arm. Therefore, our aim will be to randomize a total of 200 participants.

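### The primary model is over-parameterised: a participant random intercept cannot be identified alongside an unstructured residual matrix, and the SAP fixes no rule for what to fit instead

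*SAP*

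**What the plan says.** All of this is in the SAP, section Primary Outcome Analysis, unless another section is named.

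- Estimation: "a LMM will be fitted using restricted maximum likelihood (REML) estimation".
- Random effect: the model has "a random intercept for each participant to account for within-subject correlations". The equation carries it as a separate term u_i, defined as "Random intercept for participant i".
- Residuals: "an unstructured covariance matrix will be applied to the residuals in the LMM". The stated reason is within-subject correlation across unequally spaced visits.
- Baseline: "The primary model includes baseline scores as covariate", yet time is coded with "3 dummies: midtreatment, posttreatment, 6-month follow-up; baseline = reference". The intercept and the group coefficients are defined as baseline quantities, which implies a baseline row in the outcome vector.

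No constraint, convergence rule or fallback structure is given. General principles names R 4.4.2 but no fitting function. Secondary and Tertiary Outcome Analyses applies similar methodology to the other continuous outcomes, so they inherit the specification.

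**The concern.** The random intercept and the residual matrix are given the same job, to carry the within-person correlation. A model with both has no unique solution for its covariance parameters at any sample size.

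An analyst who meets a convergence failure has to drop one of the two written terms. Dropping the intercept leaves an unstructured model. Dropping the matrix leaves compound symmetry, with equal variance at every visit and equal correlation between all pairs. The SAP does not say which to drop, so the covariance model behind the primary standard errors is not fully fixed in advance.

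The time coding adds a second problem. If baseline is both covariate and outcome row, deleting the random intercept alone does not make the model estimable.

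**Working it through.** **1. The plan's own figure.** Inputs from Sample Size Calculation: two-sided alpha 0.05, power 0.80, effect size 0.5, correlation 0.45, three follow-ups, 20% attrition.

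- One measurement: n = 2 × ((1.96 + 0.8416)/0.5)² = 62.79 per arm.
- Mean of three follow-ups: variance factor (1 + 2 × 0.45)/3 = 0.6333.
- 62.79 × 0.6333 = 39.8, so 40; 40/0.8 = 50 per arm.

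This reproduces the stated 50 and does not depend on the present point.

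**2. Parameter count.** With T outcome occasions the marginal covariance is V = s²J + R, where s² is the intercept variance, J a matrix of ones and R the unstructured residual matrix. V has T(T+1)/2 distinct elements, and the written model has one parameter more.

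| Occasions | Parameters | Distinct elements of V | Rank |
|---|---|---|---|
| T = 3 (T2, T3, T6) | 1 + 6 = 7 | 6 | 6 |
| T = 4 (with baseline) | 1 + 10 = 11 | 10 | 10 |

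Replacing (s², R) by (s² + c, R − cJ) leaves V unchanged, so the REML likelihood is flat in that direction.

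**3. What the flat direction does to the treatment effect.** Contrasts and model-based standard errors depend on V, not on its split. This was checked on one simulated data set with T = 3, 40 per arm and about 20% dropout. The covariance was assumed (variances 1, 1.2, 1.4; covariances 0.55, 0.40, 0.60), so the sizes are only illustrative. The contrasts are one active arm against waitlist.

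| Fit | −2 REML log-likelihood | T2 contrast (SE) | T6 contrast (SE) |
|---|---|---|---|
| Unstructured, s² fixed at 0, 0.1, 0.2 or 0.3 (identical) | 1217.89 | −0.5458 (0.2149) | −1.0586 (0.2692) |
| Random intercept only | 1229.02 | −0.5452 (0.2352) | −1.0587 (0.2525) |

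The split makes no difference. The choice between the two structures does: the random-intercept-only SE is larger at T2 and smaller at T6.

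**4. Size if the random-intercept-only model were chosen.** That model uses one common variance. Approximate error of a nominal 5% test at one visit = 2 × (1 − Φ(1.96 × √(mean variance / true visit variance))). The SD ratios are assumed, because the SAP gives none.

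- SDs 1:1.1:1.2 give variances 1, 1.21, 1.44, mean 1.217. T2: 1.96 × √1.217 = 2.162, error 3.1%. T6: 1.96 × √(1.217/1.44) = 1.802, error 7.2%.
- SDs 1:1.2:1.4 give variances 1, 1.44, 1.96, mean 1.467. T2: 1.96 × √1.467 = 2.374, error 1.8%. T6: 1.96 × √(1.467/1.96) = 1.696, error 9.0%.

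**5. The baseline row.** With a baseline outcome row, the written mean model at baseline is β0 + β1 × Baseline + group effect. Setting β1 = 1, β0 = 0 and the group effects to 0 makes every baseline residual exactly zero. As the baseline variance v goes to 0, −2 REML log-likelihood changes as (N − 5) × ln v, because five mean parameters (β0, β1 and three group effects) are fixed by the baseline rows. It falls without limit. With N = 200, each tenfold drop in v lowers it by 195 × 2.303 = 449. In a simulated example it fell from 398 to −1703.

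**6. Without the baseline row, the current coding fails in another way.** The equation has 17 mean coefficients (1 + 1 + 3 + 3 + 9). T2, T3 and T6 in four arms plus one baseline slope support 4 × 3 + 1 = 13. An intercept plus three time dummies is collinear on three occasions.

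**The case against.** The strongest reply is that the redundancy is harmless. Only the split is unidentified, the marginal model is an ordinary unstructured one, and a program that stops anywhere on the flat ridge gives the right contrasts and standard errors. That stands, as step 3 shows.

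The reply adds that the SAP gives a reason for the unstructured matrix (unequal spacing). An analyst faithful to the text would therefore drop the random intercept and change nothing. This is the better reading, but the SAP does not state it as a rule, and the random intercept is also given a purpose in the text.

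A reader might infer three stronger things, which the document does not support:

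- *That the covariance model must be changed after unblinded data are seen.* Deleting the random intercept needs no data and can be done now. The SAP does not say whether such choices would be made blinded, and it provides for consulting an independent statistician throughout.
- *That the primary test would run at 1.8% to 9.0%.* Those rates are for unadjusted single-visit tests. Under Study Objectives the primary question is the effect over time and the separate visits are secondary; visit comparisons are Bonferroni-corrected.
- *That random-intercept-only is the natural fallback.* The SAP's own rationale argues against it.

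**Conclusion.** The point holds as a specification error. The random-intercept variance and the unstructured residual matrix cannot both be estimated, with one surplus parameter whether there are three occasions or four. This is exact and needs no assumption. It reaches every continuous outcome analysed by the same method.

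The consequence is conditional. A converged fit with a well-defined maximum in V gives the same inference as the plain unstructured model. Harm arises only if the fit fails and the analyst turns to compound symmetry. The single-visit error rates then rest on assumed SD ratios, and no figure is available for the over-time primary test.

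The time coding makes the correction more than the deletion of one term. Read literally, with baseline as both covariate and outcome row, the unstructured likelihood has no maximum even after the random intercept is removed. The model should be corrected before analysis; the sample size is unaffected.

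**What to change.** For continuous outcomes:

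1. Delete u_i from the equation and the text, and keep the unstructured residual matrix. This leaves the marginal covariance model unchanged.
2. Use only T2, T3 and T6 as outcome rows, with baseline solely as covariate.
3. Recode time to two dummies with T2 as reference, and let the time and interaction sums run over two terms.
4. Redefine the coefficients. The group coefficients become baseline-adjusted differences from waitlist at T2, and the interactions become changes in that difference at T3 and T6. The sentence interpreting the interaction needs matching wording, because the treatment effect at T3 or T6 is then the group coefficient plus the interaction.
5. State one ordered fallback structure for non-convergence, and name the R function and the degrees-of-freedom method. The particular order and method are for the sponsor to choose.

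The random intercept may stay in the logistic mixed model for PTSD diagnosis, where no unstructured residual matrix is specified. The cost is edits to the model equation, time coding and coefficient definitions in the SAP, plus a sentence or two for item 5. No data are needed and recruitment does not change.
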